### 3.2.3 Pharmacokinetic (PK) Population

The PK Population is defined as all patients who receive at least 1 dose of study drug and have at least 1 measured concentration for at least 1 of the analytes. The PK Population will be used for PK analyses.

### 3.2.4 *Pharmacodynamic (PD) Population*

The Pharmacodynamic Population is defined as all patients who receive at least 1 dose of study drug and have at least 1 evaluable pharmacodynamic sample. The Pharmacodynamic Population will be used for Pharmacodynamic endpoint analyses.

### 3.2.5 *Immunogenicity Population*

The Immunogenicity Population is defined as all patients who receive at least 1 dose of study drug and have at least 1 evaluable immunogenicity sample. The Immunogenicity Population will be used for immunogenicity endpoint analyses.

## 3.3 Patient Data and Study Conduct

### 3.3.1 *Patient Disposition*

Numbers and percentages of patients who were screened and screen failures will be summarized in total based on all screened patients. Reasons for screen failure will also be summarized.

Numbers and percentages of randomized patients (regardless of whether they receive study drug) and the patients in each analysis population will be summarized in total based on all randomized patients. Reasons for exclusion from each analysis population will also be summarized.

Numbers and percentages of patients in the following categories will be summarized based on the Safety population:

- Patients who discontinued study
- Patients who permanently discontinued ANV419
- Patients who permanently discontinued pembrolizumab
- Patients who permanently discontinued ipilimumab before completing 4 cycles

Reasons of discontinuation will also be presented.

Time on treatment (months) will be computed as (Date of the last dose administered – Date of first dose of study drug + 1) \* 12/365.25.

Time on study (months) will be defined as the time the patient was followed and will be computed as (Date of end of study – Date of first dose of study drug + 1) \* 12/365.25.

Time on treatment, as well as the time of study, will be summarized based on the Safety population.

Patient disposition data will be listed by patient.

### 3.3.2 *Protocol Deviations*

The protocol deviations will be reviewed by the study team and classified as “CSR Reportable” or “CSR Non-Reportable”. The number and percentage of patients with CSR Reportable protocol deviations will be summarized by category for the Safety Analysis Set.

CSR reportable protocol deviations will be listed by patient.

### 3.3.3 Demographic and Baseline Characteristics

The following demographic and baseline characteristics will be summarized by arm in part 1 & part 3 and by dose level in part 2.

- Age at informed consent (years)
- Sex
- Childbearing potential
- Race
- Ethnicity
- Height (cm)
- Weight (kg)

Demographic and baseline characteristics data will be listed by patient.

### 3.3.4 Cancer History

The following primary cancer history information will be summarized using descriptive statistics based on the Safety population:

- Histology of Primary Melanoma at initial diagnosis.
- Distant Metastasis stage at study entry based on 5 categories: M0, M1a, M1b, M1c and M1d using AJCC edition 8
- Time from initial histologic/cytologic diagnosis to study entry (months) calculated as (Date of ANV419 administration– Date of initial diagnosis+1) \* 12/365.25.
- Time from last disease progression to study entry (months) calculated as (Date of ANV419 administration– Date of last progression+1) \* 12/365.25.
- ECOG performance status at baseline (0, 1)
- BRAF mutation status based on two categories: Normal (Wild type), BRAFV600x mutated
- Brain metastasis status (Yes or No)
- Sum of diameters of target lesions at study entry
- Lactate dehydrogenase values at study entry (Screening)
- Lactate dehydrogenase levels compared to normal range at study entry (Screening) expressed as overall mean and categorical based on the following categories:
  - < 1 × ULN
  - ≥ 1 × ULN < 1.5 × ULN
  - ≥ 1.5 × ULN ≤ 2 × ULN
  - > 2 × ULN

### 3.3.5 Prior Cancer Treatment

Prior cancer treatment, including (1) prior systemic cancer therapy, (2) prior cancer radiation therapy and (3) prior cancer surgery will be recorded on this eCRF.

The mean number of lines of therapies received in the metastatic setting will be reported.

The numbers and percentage of patients with any lines of prior systemic cancer therapy will be reported categorical as following

- 1, 2, 3 or  $\geq 4$  lines of therapy,
- Adjuvant line
- Metastatic lines as 1, 2, 3 or  $\geq 4$

Note that recent adjuvant treatment will be considered as a line of therapy in the metastatic setting if the patient experienced relapse/progression on therapy within 1-year prior C1D1, or within 6 months from adjuvant therapy completion and within one-year prior C1D1.

The number and percentage of patients who received a PD-1/PD-L1 or a PD-1/PD-L1 containing regimen as last treatment prior study entry.

The number lines of prior systemic cancer therapy, the best overall response of the last prior line of therapy will be summarized based on the Safety population.

The number and percentage of patients with prior cancer radiation and prior cancer surgery will be summarized.

The reported cancer therapy terms will be coded using WHO Drug Dictionary (Global B3 March 2022 or higher). Prior cancer therapies/medications will be summarized by Anatomical Therapeutic Chemical (ATC) levels and preferred term. A patient will be counted only once within an ATC classification but may contribute to two or more preferred terms in the same classification.

### *3.3.6 Medical History*

Medical history will be collected at screening. The reported medical history term will be coded to system organ class and preferred term using the Medical Dictionary for Regulatory Activities (MedDRA) version 25.0 or higher.

Medical history data will be listed by patient.

### *3.3.7 Prior and Concomitant Non-cancer Medications*

The used prior or concomitant non-cancer medications will be recorded in the electronic case report (eCRF) from 28 days prior to Cycle 1 Day 1 to the Safety Follow-Up Visit up to 90 days after last dose of study drug or the start date of a new cancer regimen, whichever is shorter.

Prior and Concomitant medications will be coded to anatomical therapeutic chemical (ATC) class and preferred term using the WHODrug Dictionary version Global B3, March 2022 or higher.

Numbers and percentages of patients taking prior and concomitant medications by ATC class and preferred term will be summarized for each arm by dose level in the Combination Dose Finding part of the study and by treatment arm in the Monotherapy Dose Expansion part and Combination Dose Expansion part and overall using descriptive statistics based on the Safety population.

All prior and concomitant non-cancer medication data will be listed by patient.

### 3.3.8 Study Drug Exposure

Exposure of ANV419, pembrolizumab and ipilimumab (only for part 2 and part 3) will be summarized.

For each component of the study treatment to following exposure parameters will be summarized for each arm by dose level in the Combination Dose Finding part of the study and by treatment arm and BRAF mutation status in the Monotherapy Dose Expansion part and Combination Dose Expansion part and overall based on the Safety population.

- The duration of exposure (days) = date of the last dose of study drug – date of the first dose of study drug + 1. The duration of exposure (months) = duration of exposure (days) \* 12/365.25
- The total number of treatment cycles initiated. [REDACTED]
- The total dose administered
- The Actual Dose Intensity (ADI) administered (mcg/day) computed as:  
$$ADI = \frac{\text{Actual total dose administered (mcg)}}{\text{Duration of exposure (days)}}$$
- The Planned Dose Intensity (PDI) (mcg/day) computed as:  
$$PDI = \frac{\text{Total Planned dose (mcg)}}{\text{Duration of exposure (days)}}$$
- The Relative Dose Intensity (RDI) (%) computed as:  
$$RDI = \frac{ADI}{PDI} \times 100$$
- Number and percentages of patients with dose interruption and reasons of interruption

All information collected on the electronic case report form (eCRF) related to study treatment will be listed by patient.

[figure not shown]

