5.4.5 Dose Modification Guidelines

AEs (both serious and non-serious) potentially related to ANV419, pembrolizumab, or ipilimumab may represent an immunologic etiology. These AEs may occur shortly after the first dose or several months after the last dose.

If a patient experiences TEAEs that may be related to ANV419 alone or in combination with pembrolizumab or ipilimumab, ANV419 doses might be reduced if applicable, interrupted, or permanently discontinued and all changes must be reported in the Case Report Form (CRF). All ≥Grade 3 AEs considered possibly, probably, or definitely related to study drug(s) must be

discussed with the Investigator and Sponsor. During Cycle 1, dose interruption should be avoided if a patient has not experienced a ≥Grade 2 TEAE related to study drug. In subsequent cycles, dose interruptions and/or discontinuation are permissible following discussion between the Investigator and the Sponsor or designee.

5.4.5.1 Dose Modification and Management Guidelines for adverse events related to ANV419 in Monotherapy Arms

General principles

Common adverse events that have been reported with ANV419 include, but are not limited to pyrexia, liver enzyme elevations, lymphopenia, nausea/vomiting, and low-grade CRS. Appropriate supportive care or pre-medication is recommended to manage ANV419 related side effects, and to maintain ANV419 dose-intensity.

For patients enrolled in Arm A1 (), dose reduction is not permitted but modification of infusion rate and/or dose delay is allowed in the event of ANV419 related toxicities. For patients enrolled in Arm A2 (), dose reduction to is permitted in addition to modification of infusion rate and/or dose delay. Dose re-escalation of ANV419 to the randomized dose can be considered for AEs that are self-limiting and under close monitoring. If re-escalation is not tolerated, then ANV419 should be reinstated at reduced dose.

Treatment may be delayed for up to ______ to allow for resolution of ANV419 related toxicities and for up to ______ for non-ANV419 related/unexpected toxicities (i.e., hip fracture). If treatment cannot be resumed within this time frame, the patient will be permanently discontinued from study.

The section below provides specific guidelines for the management of related ANV419 toxicities. The recommendations are not intended to serve as rigid guidelines or to replace clinical judgement.

Pyrexia

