APPENDIX A: SCHEDULE OF PROCEDURES

Table 20. Schedule of Procedures for Patients Enrolled in Arms A1 or A2 (Monotherapy)

Table 20 . Sched	ule of 1	roceat	ires fo	or Pat	ients	Enroi	iea in E	Arms	A1 or	AZ (I	viono	tnerap)y)							
Week	-4 t	o -1		1		2	3		5	7	9	9	11	13	14-23	24-52	53- 105	EOS b	SF U Vi sit ^c	Sur viva 1 FU (Q1 2W)
Cycle	SCR ^a	BLª		C	C1		C2	2	С3	C4	С	25	С6	C7	C8 to C12	C13- C26	C27- C53			
	-28 to	-3 to																		
Day e	-3	-1	D1																	
Informed consent	X X	37	37																	
Eligibility criteria Demographic information ^f	X	X	X																	
Medical/ surgical history	X	X																		
Histology report (mutation status)	X																			
Vital signs ^g Physical examination ^j Body weight (kg)		_																		
ECOG PS	X																			
12-lead ECG ⁿ	X																			
Safety laboratory (local) ^{o, p} Viral Serology ^q Thyroid hormones ^r	X X X																			
Randomization			_																	

Week	-4 t	o -1		1		2	3		5	7		9	11	13	14-23	24-52	53- 105	EOS b	SF U Vi sit ^c	Sur viva 1 FU (Q1 2W)
Cycle	SCR ^a	BLa		C	C1		C	2	СЗ	C4	C	25	C6	C7	C8 to C12	C13- C26	C27- C53			
	20																			
Day ^e	-28 to	-3 to	D1																	
Pregnancy test ^t	-3 X	-1 X	וע						X		X			X	Xt	X ^t	X ^t	X	X	
CT scan ^u	Xu	A							Λ		Λ			Λ	11	Λ		Λ	Λ	
Disease evaluation (RECIST) u Cytokine samplingw PBMC samplingw ADA samplingec Biomarker sampling Immune-profile sampling ff ctDNA sampling Tumor biopsyhh ANV419 infusion ii, jj Post infusion monitoring	X																			
(90 minutes) kk Aes ^{ll}	X	X	X	X	X	X	X	X	X	X	X	X	X	X	X	X	X	X	X	
Prior/ concomitant medications Survival	X	X	X	X	X	X	X	X	X	X	X	X	X	X	X	X	X	X	X	X

a. If Screening assessments were performed within 72 hours of Cycle 1 Day 1 (C1D1), it can be combined with baseline visit and the assessments will only be done once. The baseline visit is to be conducted within 3 days from dosing unless otherwise specified.

- b. The EOS Visit is 730 days after C1D1 OR ≤30 days since last dose of study drug. This will also be the same visit with the same assessments for patients who discontinue the study early.
- c. A SFU visit will be made ≤90 days since the last dose of study drug for safety purposes.

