- t. Female patients of childbearing potential must have a negative serum pregnancy test at the Screening Visit and negative (urine or serum) pregnancy test within 72 hours prior to study Day 1. If the urine test is positive or cannot be confirmed negative, a serum pregnancy test will be required and must be negative for the patient to be eligible.
- u. Imaging performed prior to signing consent can be used for screening purposes if done within 8 weeks from signing consent. Baseline disease assessment using CT imaging (including brain assessment) is to be performed within 21 days of baseline.
- v. CT scan is not required at EOS if available within 4 weeks prior to the EOS Visit.
- w. If warranted for additional safety assessments, additional samples can be collected by the Investigator after discussion with the Sponsor. For patients who discontinue for reasons other than progressive disease, PK/ADA samples will be collected during post-treatment follow-up disease status until disease progression.
- x. To be collected pre-dose and then 2 (± 30 minutes) and 4 hours (± 1 hour) post end of infusion of ANV419.
- y. PK samples to be drawn pre-dose and then 15 minutes (±5 minute), 1 hour (±30 minutes), 2 hours (±30 minutes), 4 hours (±1 hour), and 8 hours (±1 hour) post end of infusion.

- z. PK samples to be drawn 24 hours (± 1 hour) post end of infusion.
- aa. PK samples to be drawn 72 hours (±1 hour) post end of infusion.
- bb. PK samples to be drawn pre-dose and then 1 hour (±30 minutes), and 2 hours (±30 minutes) post end of infusion.
- cc. Samples to be drawn pre-dose.
- dd.
- ee. All ADA samples to be taken pre-dose. Additional samples will be taken in the case of an IRR or irAE to rule out involvement of ADA.
- ff. If warranted for an additional PD assessment or if a PD visit is missed, an additional blood sample can be collected by the Investigator at a later visit after discussion with the Sponsor.
- gg. To be drawn
- hh. Tumor biopsies for research purpose may be performed within ± 3 days of the imaging assessment and within 7 days of the start of the dosing cycle if deemed safe and clinically feasible. Any tissue that is suspected to contain tumor, including lymph nodes, may be biopsied. All biopsies are optional.
- ii. Acetaminophen 1 g may be given to the patients as pre-medication or following the ANV419 infusion and can be used every 8 hours as needed.
- jj. A treatment interval of at least 12 days is required.

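### Actual dose intensity in SAP 3.3.8 leaves out the interval covered by the last dose, so mcg/day is overstated for early stoppers; relative dose intensity rests on an undefined planned dose

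*SAP*

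**What the plan says.** SAP 3.3.8 (Study Drug Exposure) sets "The duration of exposure (days) = date of the last dose of study drug" minus the first-dose date, plus 1. It then defines three quantities.

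- "The Actual Dose Intensity (ADI) administered (mcg/day) computed as": total dose actually given divided by that duration.
- "The Planned Dose Intensity (PDI) (mcg/day) computed as": total planned dose divided by the same duration.
- "The Relative Dose Intensity (RDI) (%) computed as": ADI over PDI, times 100.

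The readable text does not say how the total planned dose is counted. A redaction follows the item on treatment cycles initiated in the same list, so a definition may exist that cannot be seen. The section also asks for total dose, cycles initiated, and patients with dose interruption and the reasons.

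For monotherapy the protocol sets a minimum spacing (Appendix A, footnotes to Table 20): "A treatment interval of at least 12 days is required". Delays are allowed. For Arm A1, Protocol 5.4.5.1 states that "dose reduction is not permitted but modification of infusion rate and/or dose delay is allowed in the event of ANV419 related toxicities"; Arm A2 may also have a dose reduction.

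SAP section 5 drops Parts 2 and 3 and the Part 1 iRECIST analysis. It does not drop Part 1 exposure.

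**The concern.** A rate in mcg/day needs a denominator that covers the time the doses were meant to cover. Here k doses are divided by k − 1 intervals plus one day. A patient who stops after one infusion is treated as having had one day of exposure, so the whole dose becomes the daily intensity. Two patients dosed identically and on schedule get different ADI values only because one stayed on treatment longer.

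RDI raises a separate issue. Because ADI and PDI share a duration, time drops out of the ratio, and whether a delay lowers RDI depends wholly on how the planned dose is counted. Arm A1 may have delays but not reductions, while Arm A2 may have both, so a definition that registers reductions but not delays would treat the two arms differently.

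At stake is the accuracy of the ADI table, and what RDI can be taken to mean, for the two Part 1 dose levels.

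**Working it through.** The SAP gives formulas but no numerical dose intensity, so there is no stated figure to reproduce.

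**Dosing interval.** Table 20 starts Cycles 1 to 7 in weeks 1, 3, 5, 7, 9, 11 and 13, so each cycle is 7 × 2 = 14 days. As a check, it places Cycles 27 to 53 in weeks 53 to 105. Fifty-three doses 14 days apart put the last on day 14 × 52 + 1 = 729, which agrees with "The EOS Visit is 730 days after C1D1 OR ≤30 days since last dose of study drug".

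**ADI.** For k on-schedule doses at interval τ:

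- SAP duration = τ(k − 1) + 1
- duration including the last interval = τk
- overstatement = τk / (τ(k − 1) + 1)

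With τ = 14:

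| Doses | SAP days | Full days | Overstatement |
|---|---|---|---|
| 1 | 1 | 14 | 14.0 |
| 2 | 15 | 28 | 1.87 |
| 3 | 29 | 42 | 1.45 |
| 4 | 43 | 56 | 1.30 |
| 10 | 127 | 140 | 1.10 |
| 53 | 729 | 742 | 1.02 |

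At the 12-day minimum interval the factor is 12.0 for one dose and 24/13 = 1.85 for two.

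**RDI.** Let A be the dose given, P the planned total and d the duration. RDI = (A/d) / (P/d) = A/P, so d cancels and the ADI inflation does not carry over.

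**Delay example.** This case is constructed for illustration: four full doses D every three weeks, on days 1, 22, 43 and 64.

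- P = D × cycles initiated = 4D. RDI = 4/4 = 100%.
- P = D × doses scheduled in the elapsed time (days 1, 15, 29, 43 and 57) = 5D. RDI = 4/5 = 80%.
- Time-based: duration = 63 + 14 = 77 days and PDI = D/14. RDI = (4/77) × 14 = 56/77 = 73%.

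**A short delay.** Take two doses, on days 1 and 22. Two doses were scheduled by day 22 (days 1 and 15), so both definitions of P give 100%. The time-based figure is 2 × 14 / (21 + 14) = 28/35 = 80%.

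**Changing only one formula is not enough.** Suppose PDI became D/14 while duration stayed at last − first + 1. A single-dose patient would score D / (D/14) = 1400%. Four doses on days 1, 15, 43 and 57 (one 14-day delay) would score (4/57) × 14 = 98%. With both changes the second case gives (4/70) × 14 = 80%.

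**The case against.** The strongest reply is that little depends on these numbers. SAP 3.1.4 plans no formal hypothesis testing, the trial stopped after Part 1 with no responses, and no decision rule uses ADI or RDI. Delays and early stopping are reported elsewhere: interruptions with reasons and by-patient treatment listings in SAP 3.3.8, time on treatment and reasons for discontinuation in 3.3.1, and adverse events leading to interruption, reduction or discontinuation in 3.8.1.1. All of this stands and limits the consequence, although a count of interruptions does not measure how much intensity was lost.

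It also stands that 14-fold needs exactly one dose, and the documents do not say how many patients had only one.

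Three stronger readings are tempting, and the documents do not support them.

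- *A reader might infer that ADI ranks patients by how early they stopped rather than by drug received.* Between four and ten on-schedule doses the distortion is only 1.30/1.10 = 1.18-fold. The two dose levels are redacted, so the artefact cannot be compared with the true difference between arms.
- *A reader might infer that RDI as written hides delays.* That holds for every pure delay only if planned dose is counted per initiated cycle. If scheduled doses are counted, the four-dose example shows 80%.
- *A reader might infer that tolerability would be misread.* The separate tabulations listed above argue against that.

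None of this makes the ADI denominator correct.

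**Conclusion.** The point holds for ADI as written. Following SAP 3.3.8 exactly would report Part 1 mcg/day values that are too high: 14-fold for one dose (12-fold at the 12-day minimum), at most 1.87-fold from two on-schedule doses at 14-day spacing, and 1.10-fold by ten. At a constant dose the reported ADI falls as treatment continues.

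For RDI the conclusion is conditional. The ratio is free of the ADI inflation, but its meaning depends on a planned total that the readable text leaves undefined. The same delayed course can score 100% or 80%, against 73% on a time basis.

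The multipliers assume a 14-day cycle, inferred from Table 20, and on-schedule dosing. The effect is confined to descriptive Part 1 exposure summaries. ORR and the incidence of safety events are unaffected. The correction is worth making because the ADI formula gives wrong values, but it does not change the trial's conclusions.

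**What to change.** In SAP 3.3.8:

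1. For dose intensity only, use duration = last dose date − first dose date + planned cycle length (14 days in Part 1, to be confirmed against the unredacted schedule).
2. Set PDI = assigned dose per cycle / planned cycle length, so that it comes from the schedule and not from the patient's own elapsed time.
3. Keep RDI = ADI / PDI × 100. Total planned dose is then no longer needed; if it is kept for another summary, define it.
4. Keep last − first + 1 for duration of exposure and for time on treatment in SAP 3.3.1.

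The duration and PDI changes must be made together, as the working shows. The cost is two formulas in the SAP and the matching programming. No new data are needed, and nothing in the conduct of the trial or in patient management changes.

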## 3.4 Efficacy Assessment

All tumor response assessment will be assessed locally by the Investigator using RECIST 1.1 criteria and iRECIST criteria (see protocol Appendix C and D).

Baseline disease assessment will include radiographic tumor measurements using CT imaging of the chest, abdomen, pelvis, or any other areas with suspected disease involvement and CT or MRI of the brain during Screening.

For Monotherapy therapy arms, on-study disease assessment should be performed [REDACTED]

[REDACTED]

Unless otherwise noted, efficacy analyses described in this section will be performed using the Efficacy population. Summarized results will be presented for each arm by dose level in the Combination Dose Finding part of the study and by treatment arm in the Monotherapy Dose Expansion part and Combination Dose Expansion part and overall.

